3.2.3 Sample collection, storage and transportation

Sample collection

Meet the hospital-based FNA puncture standard

Sample storage and transportation

Immediately after puncture, specimens should be placed in RNAlater protective solution. It is recommended that solid substances be isolated and tested immediately. Otherwise, it should be stored at 2 - 8 °C for no more than one month; for long-term storage, it is recommended that the isolated solid substances be stored at a temperature no higher than -70 °C for no more than one year.

3.2.4 Sample numbering

In principle, only one sample should be collected from one subject, and each enrolled sample of the two detection methods should have a unique clinical trial number (secondary code). After sample enrollment, before sample detection, the blinding personnel will mark the secondary code outside the DNA sample tubes according to the blinding table, prepare the Blinding Records and carefully record the comparison table between the primary code (subject enrollment number) and the secondary code as the blind codes. Blinding documents shall be kept independently by the blinding

personnel until breaking of blindness.

During experimental procedures, only the secondary code of samples is reflected.

3.3 Study Duration and Reasons for Determination

This clinical study will last about 12 - 36 months from drafting protocol, project establishment, ethical review, agreement signing, specimen collection, detection until the end of experiment, report completion and stamping. If samples are collected smoothly and the sample size meets the trial requirements, the trial duration can be shortened; if it doesn't go smoothly, the duration can be extended appropriately.

4 Statistical Method

4.1 General Principles of Statistical Analysis

SAS 9.4 or above software will be used for statistical analysis. The sample size is calculated with PASS16. The statistical analysis of the validity and accuracy of test results is based on full analysis set (FAS) and per protocol set (PPS), and the safety analysis is based on safety set (SS). All statistical tests will be conducted on both sides and $P \leq 0.05$ will be considered statistically significant. (Unless otherwise specified)

The quantitative variables are expressed as mean, standard deviation, median, minimum, maximum, lower quartile (Q1) and upper quartile (Q3), while the categorical variables are expressed as the number and percentage of each category.

4.2 Basic clinical information of enrolled samples

Descriptive statistics is collected for the basic information and data of the population corresponding to included samples. The descriptive statistics of age, sex and disease follows the general principle.

4.3 Positive, Negative and Total Coincidence Rates Between Test Reagent and Comparison Method

For each genetic locus, fourfold tables will be used to calculate the positive and negative coincidence rates, positive and negative predictive values, total coincidence rate and their 95% confidence intervals. Using statistical software, Kappa test is used to determine statistical significance of the two methods.

Table 1 Result Summary of Clinical Trial Comparing Test Reagent and Comparison Method

Test Reagent	Comparison Method		Total
	Positive	Negative	
Positive	A	B	A+B
Negative	C	D	C+D
Total	A+C	B+D	A+B+C+D

Samples with mutant genotype detected are considered as positive, and samples without mutant genotype are considered as negative.

The calculation formula is:

$$\text{Positive coincidence rate} = A/(A+C) \times 100\%$$

$$\text{Negative compliance rate} = D/(B+D) \times 100\%$$

$$\text{Positive predictive value (PPV)} = A/(A+B) \times 100\%$$

$$\text{Negative predictive value (NPV)} = D/(C+D) \times 100\%$$

$$\text{Total coincidence rate} = (A+D)/(A+B+C+D) \times 100\%$$

The calculation formula of 95% confidence interval: $p \pm 1.96 \times [p(1-p)/n]^{1/2}$ (where P represents positive and negative coincidence rates, positive and negative predictive values and total coincidence rate, n presents the sample size. If $p > 0.9$, Wilson score method will be used for correction).

4.4 Sensitivity, Specificity and Total Coincidence Rate of Test Reagent and Clinical Reference Standard

Table 2 Result Summary of Test Reagent and Clinical Reference Standard

Test Reagent	Gold standard		Total
	Positive	Negative	
Positive	A (true-positive)	B (false-positive)	A+B
Negative	C (false-negative)	D (true-negative)	C+D
Total	A+C	B+D	A+B+C+D

Those with pathologically confirmed thyroid cancer will be considered as positive, while those without pathologically confirmed thyroid cancer whose FNA result is non-cancer without surgery will be considered as negative.

The test reagent and comparison method will be compared, but patients who fail to provide follow-up pathological results will not be included in the comparative

statistics of test reagent and clinical reference standard.

The calculation formula is:

$$\text{Sensitivity} = A/(A+C) \times 100\%$$

$$\text{Specificity} = D/(B+D) \times 100\%$$

$$\text{Total coincidence rate} = (A+D)/(A+B+C+D) \times 100\%$$

$$\text{Positive predictive value (PPV)} = A/(A+B) \times 100\%$$

$$\text{Negative predictive value (NPV)} = D/(C+D) \times 100\%$$

The calculation formula of 95% confidence interval: $p \pm 1.96 \times [p(1-p)/n]^{1/2}$ (where P represents sensitivity, specificity, positive and negative predictive values and total coincidence rate, n presents the sample size. If $p > 0.9$, Wilson score method will be used for correction.)

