3.2 Sample Screening

3.2.1 Basis to Determine Sample and Sample Size

3.2.1.1 Sample Size of Test Performance Verification

$$n = \frac{\left[Z_{1-\alpha/2} \sqrt{P_0(1-P_0)} + Z_{1-\beta} \sqrt{P_T(1-P_T)} \right]^2}{(P_T - P_0)^2}$$

Where, n represents the sample size; $Z_{1-\alpha/2}$ and $Z_{1-\beta}$ are fractions of standard normal distribution, P_0 is the target value of the evaluation indicator, and P_T is the expected value of the evaluation indicator for in vitro diagnostic reagents.

- (1) BRAF gene: According to the results of preclinical studies, the target value of positive coincidence rate between test reagent and contrast reagent is up to 85% with the expected value up to 95%, the minimum sample size of positive control group is estimated to be 78; the target value of negative coincidence rate is up to 85% with the expected value up to 90%, the minimum sample size of negative control group is estimated to be 363 and the minimum overall sample size is 441.
- (2) TERT gene: According to the results of preclinical studies, the target value of positive coincidence rate between test reagent and contrast reagent is up to 85% with the expected value up to 98%, the minimum sample size of positive control group is estimated to be 40; the target value of negative coincidence rate is up to 85% with the expected value up to 90%, the minimum sample size of negative control group is estimated to be 363 and the minimum overall sample size is 403.

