4.6 Clinical Evaluation Standard

1) Coincidence rate: Compared to the comparison method, if the lower limit of two-sided 95% confidence interval for both positive and negative coincidence rates of BRAF and TERT genes are greater than the 85% of preset target value, the statistical hypothesis is valid and in good agreement with the comparison method; otherwise, the statistical hypothesis is invalid, and the agreement with comparison method is not acceptable.

2) Sensitivity and specificity: Compared to the clinical reference method, if the lower

limit of two-sided 95% confidence interval for the sensitivity of BRAF or TERT gene pooled detection is greater than 50% of the preset target value and the lower limit of two-sided 95% confidence interval for the sensitivity of BRAF or TERT gene pooled detection is greater than 80% of the preset target value, the statistical hypothesis is valid and the diagnostic accuracy is acceptable; otherwise the statistical hypothesis is invalid, and the diagnostic accuracy is not acceptable.

5 Quality Control Method

Quality control should be applied at every stage of the clinical trial to ensure that all data are reliable and correct. The quality control method is as follows:

- (1) Qualifications of researchers involved in the study Researchers involved in the clinical trial must have professional expertise, qualifications and competences in the clinical trial, and pass the qualification examination, and staffing should be relatively fixed.
- (2) Training and preliminary tests: The sponsor is responsible for the training of researchers before the start of clinical trial, so as to help clinical researchers fully understand the clinical trial protocol, the detection of investigational products, the filling of original records and forms, etc.
- (3) Laboratory quality control: Clinical laboratories should be strictly in accordance with the *Measures for the Administration of Clinical Gene Amplification Testing Laboratories in Medical Institutions* (MOH Office MA [2010] No. 194 or the current effective version) and other relevant administrative regulations of molecular biology laboratories and clinical gene amplification laboratories.
- (4) Only when the quality control of investigational products meets relevant requirements can the test data be valid.

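### Using the Wald interval up to an estimate of 0.9 and Wilson only above it raises the false-pass rate for specificity and negative coincidence by about half, and can pass a worse result while failing a better one

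*Protocol*

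**What the plan says.** Protocol section 4.3 gives the 95% interval for the coincidence rates and predictive values as p ± 1.96·√(p(1−p)/n), the Wald interval, and adds: "n presents the sample size. If $p > 0.9$, Wilson score method will be used for correction". Section 4.4 repeats the rule for the comparison with the clinical reference standard: "where P represents sensitivity, specificity, positive and negative predictive values and total coincidence rate, n presents the sample size. If $p > 0.9$, Wilson score".

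Section 4.6 turns the lower limit into the decision. For agreement with Sanger sequencing the criterion is the "lower limit of two-sided 95% confidence interval for both positive and negative coincidence rates of BRAF and TERT genes are greater than the 85" per cent target. For diagnostic accuracy one lower limit must exceed 50%, and a second passes if it "is greater than 80% of the preset target value". The second clause prints sensitivity again. It is read here as specificity, because section 3.2.1.2 sets the specificity target at 80%. The percentages in section 4.6 are read as the targets themselves, not as fractions of a target.

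Section 4.1 fixes the level: "All statistical tests will be conducted on both sides and $P \leq 0.05$ will be considered statistically significant". A pass that needs only the lower limit of a two-sided 95% interval therefore has a nominal false-pass rate of 2.5%.

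**The concern.** The observed result selects the interval method, and the change-over sits at 0.9, which is the planning value for both negative coincidence and specificity. For proportions between about 0.80 and 0.90 the Wald lower limit is too high. The lenient method is therefore the one in force where these two endpoints are decided.

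The limit also drops when the estimate crosses 0.9, so one more correct result can lower it. The rule does not match the plan's own sample-size formula either. That formula puts the null variance P0(1−P0) on the alpha term, which corresponds to the score test that the Wilson interval inverts.

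At stake is the error rate of the acceptance decision on two endpoints, and whether acceptance is consistently ordered by performance. A smaller point is that n is called the sample size for five rates that have different denominators.

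**Working it through.** **Inputs.** Targets, expected values and group sizes come from Protocol sections 3.2.1.1 and 3.2.1.2: negative coincidence 0.85, 0.90, 363; specificity 0.80, 0.90, 108; BRAF positive coincidence 0.85, 0.95, 78; TERT positive coincidence 0.85, 0.98, 40; sensitivity 0.50, 0.60, 194. The protocol does not state power; 80% is assumed.

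**Reproducing the plan's sizes.** The formula is n = [1.96·√(P0(1−P0)) + 0.8416·√(PT(1−PT))]² / (PT−P0)².
- Specificity: (0.7840 + 0.2525)² / 0.10² = 107.4, so 108.
- Negative coincidence: (0.6998 + 0.2525)² / 0.05² = 362.8, so 363.
- The other three give 78.02 (stated 78), 39.6 (40) and 193.8 (194).

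Two-sided 5% with 80% power thus accounts for all five stated sizes.

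**Limits at the deciding counts.** Wald: p − 1.96·√(p(1−p)/n). Wilson: [p + z²/2n − z·√(p(1−p)/n + z²/4n²)] / (1 + z²/n), with z = 1.96.
- 94/108 = 0.8704. Wald: 0.8704 − 1.96 × 0.03232 = 0.8070, a pass. Wilson: 0.7941, a fail.
- 321/363 = 0.8843. Wald: 0.8843 − 1.96 × 0.01679 = 0.8514, a pass. Wilson: 0.8473, a fail.

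Both estimates are below 0.9, so the protocol uses the Wald limit.

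**Exact pass probabilities.** For each rule, find the counts X that pass and sum their Binomial(n, p) probabilities, at p = target for the false-pass rate and at p = expected value for power.

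| Endpoint | Rule | Pass at | False-pass | Power |
|---|---|---|---|---|
| Specificity, n = 108 | as written | ≥ 94 | 3.88% | 88.0% |
| | Wilson | ≥ 95 | 2.10% | 81.0% |
| Negative coincidence, n = 363 | as written | ≥ 321 | 3.62% | 86.0% |
| | Wilson | ≥ 322 | 2.53% | 82.0% |

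Against 2.5% these are ratios of 3.88/2.5 = 1.55 and 3.62/2.5 = 1.45.

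**Other endpoints at planned size.** The rule as written and Wilson give the same cut-off. False-pass rates are 1.73% (BRAF positive coincidence), 1.21% (TERT positive coincidence) and 2.61% (sensitivity).

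**Other denominators.** At the 80% target, n = 80–239, the rule as written averages 3.9% (range 2.9–5.7%) and Wilson averages 2.1%. At the 85% target, n = 180–499, it averages 3.6% (range 2.9–5.0%) and Wilson averages 2.2%. The rule as written exceeds 2.5% at every n in both ranges; Wilson never exceeds 2.75%.

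**Order reversals.**
- At n = 108 the limit falls from 0.841 (97 correct, Wald) to 0.838 (98 correct, Wilson). Both clear 0.80, so no decision changes.
- At the 85% target, 171/191 (89.5%) has limit 0.8519 and passes; 172/191 (90.1%) has limit 0.8499 and fails. Likewise 135/150 passes (0.8520) and 136/150 fails (0.8494).
- Such pass/fail reversals occur at 15 denominators from 140 to 191 at the 85% target. At the 80% target they occur only at n = 39, 46 and 53.

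**The case against.** The arithmetic is not in dispute; the objections concern weight.

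- **Reversals.** None arises at a planned group size. For specificity they need about 39 to 53 negatives, and for negative coincidence 140 to 191, well below the planned 108 and 363. The most realistic place is BRAF positive coincidence. If mutation-positive patients are 60% of the 70% with cancer (an assumption built from the protocol's planning values), 360 to 400 patients give about 151 to 168 positives. Even then, with true agreement of 95%, the chance of landing on the failing count is about 1.0% at n = 150 and 0.5% at n = 166. At 900 patients (three sites of 300) the group would be about 378, outside the range. This stands: the reversal is a defect of the rule but an unlikely event.
- **One count.** The inflation comes from a single count at each planned size, and three of the five planned tests are unaffected. That is true, but the scan over n shows a systematic excess, not an accident of discreteness at 108 or 363.
- **Joint criteria.** Section 4.6 requires several criteria together, so 3.6–3.9% is the error for one endpoint at its target, not the general chance of wrongly accepting the kit. This stands as a description. It gives little protection when the other endpoints pass easily.
- **Meaning of n.** Each rate's formula shows its denominator, so misreading is unlikely. This part is wording only.

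**Conclusion.** The concern holds. At the planned sizes the stated rule has a false-pass rate of 3.9% for specificity and 3.6% for negative coincidence, 1.55 and 1.45 times the nominal 2.5%. The excess persists across the neighbouring denominators examined. Reversals of pass and fail are possible, but only at denominators that are not planned group sizes.

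The figures assume independent binomial results, a true rate exactly at the target, the 80% criterion in section 4.6 applying to specificity, and 80% planned power. The last assumption bears only on the power comparison. The protocol itself fixes the rule, so this is not a detail left to an analysis plan. It should be corrected before the data are analysed.

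**What to change.** In sections 4.3 and 4.4, delete the Wald formula and the switch at 0.9. State that every rate is reported with a two-sided 95% Wilson score interval regardless of the observed value, and that the criteria in section 4.6 use its lower limit. Define n as the denominator of the rate concerned: A+C, B+D, A+B, C+D, or the total.

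The cost is a short text change and standard software. Passing becomes one count harder for specificity (95 of 108 instead of 94) and for negative coincidence (322 of 363 instead of 321), with the power loss shown in the table. At exactly the planned sizes power stays above 80%. Because counts are discrete it dips slightly at some nearby sizes: 79.1% at n = 110 and 78.2% at n = 111 for specificity, and 79.5% at n = 368 and 79.0% at n = 369 for negative coincidence. The planned sample size need not change for this reason.

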The molecular mechanism of thyroid carcinogenesis and progression is the abnormal activation of intracellular signal transduction induced by related gene changes. Among these, MAPK signaling pathway is one of the important signaling pathways for thyroid carcinogenesis and progression. The missense mutation of a single base in Exon 15 of BRAF gene (GTG>GAG) causes the replacement of valine (V) corresponding to codon 600 of translation protein by glutamate (E), which becomes activated protein kinase, and induces tumor formation by activating MAPK signaling pathway. TERT promoter mutation induces the abnormal activation of telomerase, which is a key step in thyroid carcinogenesis. It has been found that ETS (E-twenty-six) protein is a transcription factor family downstream of the BRAF-MAPK signaling pathway. When TERT gene promoter mutates, it can produce some special nucleotide sequences, which can bind to ETS protein, and cause tumorigenesis by enhancing TERT gene expression. Many studies have shown that BRAF gene V600E mutation and two mutations in TERT gene promoter region (1 295 228C>T and 1 295 250C>T) are frequently observed in thyroid cancer, and the poor prognosis of thyroid cancer patients can be effectively evaluated. Further studies have confirmed that the coexistence of BRAF and TERT promoter mutations has a synergistic effect on the invasiveness of thyroid cancer, and the two mutated tumors

are related to the high recurrence risk and increased disease-specific mortality of differentiated thyroid cancer, as well as a higher mortality trend in ATC. Therefore, TERT promoter mutation and BRAF mutation can be used as molecular markers for thyroid diagnosis.

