3.1.2 Performance validation of test reagent

Among the enrolled patients, postoperative pathological results will be obtained from those who underwent surgery subsequently. Those with pathologically confirmed thyroid cancer will be considered as positive, while those without pathologically

confirmed thyroid cancer whose clinical diagnosis is non-cancer without surgery will be considered as negative. The results of the test reagents will be compared and the clinical sensitivity and specificity of the test reagents will be calculated.

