3.2.1.2 Sample Size of Diagnostic Performance Verification

$$n = \frac{\left[Z_{1-\alpha/2} \sqrt{P_0(1-P_0)} + Z_{1-\beta} \sqrt{P_T(1-P_T)} \right]^2}{(P_T - P_0)^2}$$

Where, n represents the sample size; $Z_{1-\alpha/2}$ and $Z_{1-\beta}$ are fractions of standard normal distribution, P_0 is the target value of the evaluation indicator, and P_T is

the expected value of the evaluation indicator for in vitro diagnostic reagents.

Samples with BRAF or TERT mutation detected by the test reagent are considered as positive, and samples without mutation are considered as negative.

The results of pathological examination and clinical diagnosis will be used for comparison method. Those with pathologically confirmed thyroid cancer will be considered as positive, while those without pathologically confirmed thyroid cancer whose clinical diagnosis is non-cancer without surgery will be considered as negative.

According to relevant literature reports and preclinical study results, if the target value of sensitivity for the test reagent and comparison method is up to 50% with the expected value up to 60%, the minimum sample size of positive control group is estimated to be 194. According to previous experience, the proportion of positive diagnosis upon postoperative pathological examination is generally more than 70%. If estimated as 70%, the overall sample size of prospectively enrolled patients is 278. The target specificity value is 80% with the expected value of 90%, the minimum sample size of negative control group is estimated to be 108. If the proportion of negative results obtained from the postoperative pathological examination is estimated as 30%, the overall sample size of prospectively enrolled patients is 360. For the final overall sample size calculated based on sensitivity and specificity, the larger one (360 cases) shall prevail. Considering the estimated dropout rate of 10%, the final actual overall sample size is 400.

It is planned to carry out the trial in at least three clinical sites, with the enrollment of no less than 300 samples at each site. In case of objective reasons, when the sample size is insufficient, appropriate adjustments can be made among the sites to ensure the overall sample size. If the relevant laws and regulations change during the trial, the latest laws and regulations shall prevail, and the number of samples should be statistically significant.

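### Section 4.4 gives two rules that do not fit together for patients without pathology, and counts only pathologically confirmed cancers towards sensitivity, so the 50% verdict rests on verification being unrelated to the kit result

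*Protocol*

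**What the plan says.** Pathology reaches the trial only through surgery. Protocol section 3.1.2 says that "postoperative pathological results will be obtained from those who underwent surgery subsequently".

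Section 4.4 defines reference positives: "Those with pathologically confirmed thyroid cancer will be considered as positive". For reference negatives it adds that "those without pathologically confirmed thyroid cancer whose FNA result is non-cancer without surgery will be considered as negative". Section 3.1.2 has a parallel rule based on clinical diagnosis rather than FNA: those without pathologically "confirmed thyroid cancer whose clinical diagnosis is non-cancer without surgery will be considered as negative". Section 3.2.1.2 repeats that version.

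The next paragraph of 4.4 then says that "patients who fail to provide follow-up pathological results will not be included in the comparative" statistics of the kit against the clinical reference standard.

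Section 4.6(2) requires the lower limit of the two-sided 95% interval for sensitivity to exceed 50%. Section 4.4 makes that interval a Wald interval unless the estimate is above 0.9. Section 3.2.1.2 assumes 60% sensitivity, a 70% share of cancers at postoperative pathology and 10% dropout. Section 4.1 names a full analysis set and a per protocol set without defining either.

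**The concern.** There are two linked problems.

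First, an unoperated patient with a non-cancer FNA result has no follow-up pathology. One statement in 4.4 counts that patient as a reference negative. Read literally, the next removes the patient. The composition of the negative group, and so specificity, depends on which is applied.

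Second, whichever is applied, a cancer enters A + C only if it was operated on and its pathology was returned. An unoperated cancer is either left out or, if its FNA was non-cancer, placed among the negatives. In the second case a kit-negative cancer is scored as a true negative, which flatters specificity, and a kit-positive one as a false positive. Sensitivity computed on verified cancers equals the kit's sensitivity only if verification is unrelated to the kit result among cancers. Because sensitivity decides half of 4.6(2), a departure from that condition moves the false-pass rate away from its nominal 2.5%.

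**Working it through.** **1. The plan's own figures.** The formula in 3.2.1.2 with P0 = 0.50, PT = 0.60 and two-sided 0.05 gives 193.85, hence 194 positives. With 0.80 and 0.90 it gives 107.43, hence 108 negatives. Power is not stated in the section; 80% is inferred because it reproduces the stated sizes. Then 194/0.7 = 277.1, hence 278; 108/0.3 = 360; 360/0.9 = 400. All agree with the protocol, so the sample sizes are not in error.

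**2. Expected cancers.** Applying the 70% share throughout: 400 × 0.7 = 280 enrolled and 360 × 0.7 = 252 verified, so 28 are lost.

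**3. Pass threshold.** The rule is x/n − 1.96·√[(x/n)(1 − x/n)/n] > 0.50. With n = 252, 141 gives a lower limit of 0.498 (fail) and 142 gives 0.502 (pass). With n = 194 the threshold is 111.

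**4. What complete-case sensitivity estimates.** Let p be the true sensitivity, and v1 and v0 the verification rates in kit-positive and kit-negative cancers, with r = v1/v0. Among verified cancers the kit-positive share is

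p·v1 / [p·v1 + (1 − p)·v0] = p·r / (p·r + 1 − p).

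This equals p only at r = 1.

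**5. Chance of passing at p = 0.50** (exact binomial tail at the thresholds above). r is an assumption; the protocol gives no value.

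| r | Expected observed sensitivity | 252 verified | 194 verified |
|---|---|---|---|
| 0.9 | 0.45/0.95 = 47.4% | 0.3% | 0.4% |
| 1.0 | 50.0% | 2.5% | 2.6% |
| 1.1 | 0.55/1.05 = 52.4% | 11.5% | 10.1% |
| 1.25 | 0.625/1.125 = 55.6% | 42.6% | 34.8% |

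**6. How large r can be.** At p = 0.50 and r above 1, the smallest share of cancers that must go unverified is 0.5 × (1 − 1/r): 4.5% for r = 1.1, 10% for r = 1.25 and 16.7% for r = 1.5. In counts, 280 cancers are 140 kit-positive and 140 kit-negative. If all 28 lost are kit-negative, r = 1/(112/140) = 1.25. So 1.25 is the ceiling when the 10% allowance applies to cancers and covers every unverified one.

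**7. A tipping-point example at the expected 60%.** Observed 151/252 = 59.9% has a lower limit of 53.9% and passes. If all 28 lost cancers were kit-negative, 151/280 = 53.9% has a lower limit of 48.1% and fails. If 22 were kit-negative, the other 6 are kit-positive: 157/280 has a lower limit of 50.3% and passes. If 23 were, 156/280 has 49.9% and fails. The verdict therefore turns only when at least 23 of 28 (82%) are kit-negative, against 101/252 = 40% among the verified.

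**The case against.** - **Not everyone without pathology is dropped.** A reader who stops at the exclusion sentence might infer that every such patient is removed. The preceding paragraph of 4.4 and sections 3.1.2 and 3.2.1.2 keep unoperated non-cancer patients as negatives. This stands. Those who clearly leave the comparison are unoperated patients not classed as non-cancer, and patients whose pathology was not returned.
- **Upward bias is not shown.** A reader might infer it from the background statement that "the coexistence of BRAF and TERT promoter mutations has a synergistic effect on the invasiveness of thyroid cancer". That statement concerns coexisting mutations and invasiveness, not surgery rates, and the kit calls either mutation positive. Samples are coded and tested blind (3.1.1, 3.2.4), which argues against the kit result driving surgery. This stands as to direction. An indirect link, for instance through clearer cytology in mutated cancers, can be neither confirmed nor excluded from the protocol.
- **Large values of r do not fit the plan.** r = 1.5 would give an expected 60% and an 89% chance of passing with 252 cancers, but it needs at least 16.7% of cancers unverified. It should not be quoted as an effect of the planned loss.
- **The SAP is not shown.** It may define the full analysis set and contain analyses for missing reference results, so their absence from the protocol is no finding. The exclusion rule and its conflict with the adjacent statement are, however, fixed in the protocol itself.
- **A corrected estimate need not be better.** Begg-Greenes or inverse-probability weighting is not identified in strata without verified patients, and it assumes that verification is random within strata. This stands against making it the deciding criterion, but not against supportive use.

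**Conclusion.** The point holds in a limited form. The two statements in 4.4 conflict for unoperated patients with a non-cancer FNA result. On either reading sensitivity is a complete-case estimate among verified cancers. If kit-positive cancers are verified 10% more often in relative terms, a kit exactly at the 50% target passes 11.5% of the time instead of 2.5%; at the 10%-loss ceiling of r = 1.25 it is about 43%. If they are verified less often (r = 0.9), the chance falls to 0.3% and the bias works against the kit.

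These figures assume true sensitivity of 50%, 252 verified cancers, the 70% share applied to everyone enrolled, and a value of r that the protocol does not supply. They show how far the verdict depends on the exclusion. They do not show that the trial will be biased, or in which direction.

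**What to change.** In 4.4:

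- State which unoperated patients are kept as reference negatives and which are excluded, and use one definition (FNA result or clinical diagnosis) there and in 3.1.2 and 3.2.1.2.
- Keep the complete-case estimate as primary.
- Tabulate kit and FNA results for all excluded patients.
- Pre-specify best/worst-case (tipping-point) bounds for sensitivity and specificity over the unverified patients.
- Where strata contain verified patients, add a supportive Begg-Greenes or inverse-probability-weighted estimate by FNA category and kit result.

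In 4.6(2), require the conclusion to be reported as dependent on the exclusion if the verdict changes under these analyses.

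The cost is protocol wording and some programming, with no additional patients or tests. The sponsor also accepts that the conclusion may turn out less favourable or carry a qualification.

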3.2.2 Inclusion, exclusion and elimination criteria

3.2.2.1 Inclusion criteria

- (1) Patients with clinically suspected of thyroid cancer who underwent fine needle aspiration (FNA)

- (2) Samples should have appropriate basic clinical information, including: The patient's unique traceable number, age, sex, pathological diagnosis results, etc.
- (3) Subjects who can provide a complete FNA sample
- (4) Subjects who agreed to provide follow-up information

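### Section 4.4 takes PPV, NPV and total coincidence from crude Table 2 counts while contradicting itself on who enters that table, so the cancer share to which these figures apply is not fixed.

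*Protocol*

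**What the plan says.** Section 4.4 of the protocol defines PPV as A/(A+B), NPV as D/(C+D) and total coincidence as (A+D)/N from Table 2. Each gets a Wald interval, or a Wilson interval when the estimate exceeds 0.9 ("where P represents sensitivity, specificity, positive and negative predictive values and total coincidence rate"). No cancer proportion is attached to these figures and no standardisation is described.

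On who enters Table 2, section 4.4 makes two statements that do not fit together:
- Patients not operated on whose FNA result is non-cancer are classed as negative. Sections 3.1.2 and 3.2.1.2 say the same, but on the basis of clinical diagnosis.
- Immediately afterwards, "patients who fail to provide follow-up pathological results will not be included in the comparative" statistics against the clinical reference standard.

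The enrolled population in section 3.2.2.1 is "Patients with clinically suspected of thyroid cancer who underwent fine needle aspiration (FNA"), whether or not surgery follows. The only cancer share in the document is in section 3.2.1.2, and it refers to operated patients: "the proportion of positive diagnosis upon postoperative pathological examination is generally more than 70" per cent. The same section then applies it to everyone enrolled: "If estimated as 70%, the overall sample size of prospectively enrolled patients is 278". It treats the negatives likewise ("If the proportion of negative results obtained from the postoperative pathological examination is estimated as 30" per cent), which leads to 360 enrolled.

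**The concern.** Sensitivity and specificity are each calculated within one column of Table 2, so the ratio of cancers to non-cancers does not enter them. PPV, NPV and total coincidence mix the two columns and move with that ratio. The kit is intended to assist FNA, so the reader of a PPV or NPV will apply it to a patient who has just had an FNA. If the table holds only patients with surgical pathology, the figures describe a surgical series. If it also holds the unoperated non-cancer patients, they describe something close to the enrolled FNA cohort. Section 4.4 would print either set in the same form, with nothing to tell the reader which cancer share lies behind it. The intervals cover sampling error at the table's own share and say nothing about another share.

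**Working it through.** **Inputs.** Section 3.2.1.2 gives sensitivity 50% target and 60% expected ("if the target value of sensitivity for the test reagent and comparison method is up to 50% with the expected value up to 60" per cent), and specificity 80% and 90% ("The target specificity value is 80% with the expected value of 90" per cent). It also gives cancer and non-cancer shares of 70% and 30%, and dropout of 10%. Section 4.1 makes tests two-sided at 0.05. Power is not stated; 80% is assumed because it reproduces the stated sizes. No cancer share for all FNA patients is given, so shares below 70% are assumptions.

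**Step 1: reproduce the plan's sizes** with its own formula.
- Sensitivity: [1.96·√(0.5·0.5) + 0.8416·√(0.6·0.4)]² / 0.10² = 193.85, so 194. Then 194/0.70 = 277.1, so 278.
- Specificity: [1.96·√(0.8·0.2) + 0.8416·√(0.9·0.1)]² / 0.10² = 107.43, so 108. Then 108/0.30 = 360.
- Dropout: 360/0.90 = 400.

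All five figures agree. Dividing 108 by the surgical non-cancer share makes sense only if every reference-negative comes from surgery. The planning table is then 360·0.70 = 252 cancers and 108 non-cancers.

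**Step 2: the measures as functions of the cancer share p**, with Se = 0.60 and Sp = 0.90:
- PPV = p·Se / [p·Se + (1−p)(1−Sp)]
- NPV = (1−p)·Sp / [(1−p)·Sp + p(1−Se)]
- Total coincidence = p·Se + (1−p)·Sp

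| Cancer share p | PPV | NPV | Total coincidence |
|---|---|---|---|
| 70% (section 3.2.1.2) | 93.3% | 49.1% | 69.0% |
| 50% (assumed) | 85.7% | 69.2% | 75.0% |
| 30% (assumed) | 72.0% | 84.0% | 81.0% |

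**Step 3: the section 4.4 intervals under the surgical-only reading.** With 252 and 108, expected counts are A = 151.2, B = 10.8, C = 100.8, D = 97.2.
- PPV = 151.2/162 = 93.3%, Wilson 88.4–96.3%.
- NPV = 97.2/198 = 49.1%, Wald ± 1.96·√(0.491·0.509/198) = ± 7.0 points, so 42.1–56.1%.

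Neither interval contains the value at 50% or 30% cancer.

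**Step 4: the other reading.** Add unoperated non-cancer patients to the same 252 and 108, with the number assumed and Se and Sp unchanged.

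| Added | Cancer share | PPV | NPV | Total coincidence |
|---|---|---|---|---|
| 0 | 70.0% | 93.3% | 49.1% | 69.0% |
| 100 | 252/460 = 54.8% | 151.2/172 = 87.9% | 187.2/288 = 65.0% | 338.4/460 = 73.6% |
| 360 | 252/720 = 35.0% | 151.2/198 = 76.4% | 421.2/522 = 80.7% | 572.4/720 = 79.5% |

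The 70% share holds in Table 2 only if unoperated patients are left out.

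**The case against.** A reader might infer that section 4.4 certainly overstates PPV and understates NPV for FNA patients. The documents do not support that.

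- The sentence just before the exclusion puts unoperated non-cancer patients into the table as negatives. If they stay in, Table 2 is close to the prospective FNA cohort, where crude PPV and NPV are the natural estimates.
- A reading that saves both sentences would drop only patients whose status is unresolved, such as a suspicious FNA without surgery. Those patients could be likelier cancers than the average, and dropping them would move PPV and NPV the opposite way.
- No passage says that kit results play no part in who goes to surgery. Section 3.2.4 blinds sample codes and is silent on this.

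Also fair: the 252/108 table is not a fixed plan, since section 3.2.1.1 needs at least 441 samples and section 3.2.1.2 foresees at least three sites with 300 or more each. An interval that misses the value for a population with another prevalence is not thereby wrong. Table 2's column totals show its cancer share to a careful reader.

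These objections remove the claim of a known direction and size. They do not remove the point that the two readings give very different figures and that the document fixes the crude formulas without settling the reading.

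**Conclusion.** The point holds in conditional form and should be acted on. Under the literal exclusion, which the sizing arithmetic implies, the reported values would be about 93% (PPV), 49% (NPV) and 69% (total coincidence), and would belong to a surgical series. If unoperated non-cancer patients are kept, most of that shift goes. Its size for the intended-use population cannot be stated, because that population's cancer share is not given; the 30% and 50% rows are illustrations.

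The results assume the planned 60% and 90% and that both are the same in operated and unoperated patients. Leaving unoperated patients out, or taking their FNA result as the reference, could shift sensitivity and specificity as well.

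It would also be wrong to infer that the trial's conclusion is at risk from these measures. Section 4.6 judges the clinical comparison by confidence limits against 50% and 80%. It prints sensitivity for both, but the 80% target is that of specificity in section 3.2.1.2. PPV, NPV and total coincidence carry no criterion there.

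**What to change.** 1. Reconcile the two sentences in section 4.4 with each other and with sections 3.1.2 and 3.2.1.2, so that it is clear whether unoperated non-cancer patients enter Table 2 and whether clinical diagnosis or the FNA result classifies them.
2. Report the cancer share of Table 2, and label the crude PPV, NPV and total coincidence as applying at that share.
3. Add the three measures computed by the formulas above from the estimated sensitivity and specificity, at the cancer share among all enrolled patients with a determined status and over a stated grid, for example 30%, 50% and 70%. Use delta-method or bootstrap intervals. If item 1 keeps the unoperated non-cancer patients, the cohort value will nearly coincide with the crude one, and the grid does the remaining work.
4. State the assumption that sensitivity and specificity carry over to patients outside the table.

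The cost is a few lines in section 4.4 and one extra table from data already collected. The PPV shown to readers may be less favourable. The pass rule in section 4.6 needs no change on this account.
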